14.11.10.2. Part B

No.	Population	IDSL / Example Shell	Title	Programming Notes	Deliverable
Serum Target Engagement					

4.06	Safety	PD_T1	
Part B: Summary of Free & Total CCL17 in Serum Concentration-Time Data (pg/mL)
 
Please only present the median, min, max, sd (log), geometric mean and 95% CI back-transformed from the \log_e scale. Apply logit transformation for % reduction parameter. If % reduction ≤ 0, set to 0.1. If % reduction ≥ 100, set to 99.9. These imputations are needed for logit transformation. Use Student's t-distribution for CI.
 
Please only present the median, min, max, sd (log), geometric mean and 95% CI back-transformed from the \log_e scale. Apply logit transformation for % reduction parameter and present median, min, max, sd (logit), geometric mean and 95% CI back-transformed from the logit scale. If % reduction ≤ 0, set to 0.1. If % reduction ≥ 100, set to 99.9. These imputations are needed for logit transformation. Use Student's t-distribution for CI. Add the following footnotes: Note: Free CCL17 values below the LLOQ have been imputed to $\frac{1}{2}^*LLOQ$. Total CCL17 values below the LLOQ have been imputed to 0. Values equal to zero at baseline have been imputed to LLOQ whilst missing baseline values have been imputed to the median of the non-missing baseline values. Note: Free CCL17 and Total CCL17 exceeding the upper limit of quantification (ULOQ) have been excluded from the summary statistics (ULOQ Free CCL17: 3600 pg/mL, ULOQ Total CCL17: 50000 pg/mL). Note: If more than 30% of values have been imputed at any timepoint for a treatment group, then the standard deviation is not displayed. Note: Baseline is the mean of the Day -4 and Day 1 Pre-Dose assessments. Note: Percentage reduction and fold increase parameters were calculated using a model based post-hoc analysis. Note: Percentage reduction values ≤ 0 are imputed to be 0.1 and values ≥ 100 are imputed to be 99.9.
	Part B SAC
------	--------	-------	---	------------

No.	Population	IDSL / Example Shell	Title	Programming Notes	Deliverable
				Note: The percentage reduction parameter was logit transformed, summarised, and back-transformed using the logistic function to obtain the geometric summary statistics. The 95% CI of the geometric mean was calculated using Student's t distribution.	
4.07.	Safety	PD_T2	Part B: Summary of Model-Derived Free and Total CCL17 in Serum Target Engagement Parameters (non- transformed and log- transformed)	
Please only present the median, min, max, sd (log), geometric mean and 95% CI back-transformed from the \log_e scale.
 
Please note that tmin and tmax should not be \log_e-transformed and 95% CI should not be presented.
 
Apply logit transformation for % reduction and maximum % reduction parameters.
 
If % reduction ≤ 0, set to 0.1.
 
If % reduction ≥ 100, set to 99.9.
 
These imputations are needed for logit transformation.
 
Use Student's t-distribution for CI.
 
Add the following footnotes:
 
Note: All Target Engagement parameters were calculated using a model based post-hoc analysis.
 
Note: Percentage reduction values ≤ 0 are imputed to be 0.1 and values ≥ 100 are imputed to be 99.9.
 
Note: The percentage reduction and maximum percentage reduction parameters were logit transformed, summarised, and back-transformed using the logistic function to obtain the geometric summary statistics. The 95% CI of the geometric mean was calculated using Student's t distribution.
	IA3, Part B SAC
Immunogenicity					
4.08.	Safety	IMM1	Part B: Summary of Immunogenicity	Add extra row for Part B SAC - "Highest post-baseline" result. This would be #participants with at least one post-baseline positive result / # participants with at least one post baseline sample.	IA3, Part B SAC

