14.11.10. Pharmacodynamic Tables

14.11.10.1. Part A

No.	Population	IDSL / Example Shell	Title	Programming Notes	Deliverable
Serum Target Engagement					
4.01	Safety	PD_T1	Part A: Summary of Free & Total CCL17 in Serum Concentration- Time Data (pg/mL)	
Please only present the median, min, max, sd (log), geometric mean and 95% CI back-transformed from the \log_e scale.
 
Apply logit transformation for % reduction parameter and present median, min, max, sd (logit), geometric mean and 95% CI, back-transformed from the logit scale.
 
If % reduction ≤ 0, set to 0.1.
 
If % reduction ≥ 100, set to 99.9.
 
These imputations are needed for logit transformation.
 
Use Student's t-distribution for CI.
 
Add the following footnotes:
 
Note: Free CCL17 values below the LLOQ have been imputed to $\frac{1}{2}^*$ LLOQ. Total CCL17 values below the LLOQ have been imputed to 0. Values equal to zero at baseline have been imputed to LLOQ whilst missing baseline values have been imputed to the median of the non-missing baseline values.
 
Note: Free CCL17 and Total CCL17 exceeding the upper limit of quantification (ULOQ) have been excluded from the summary statistics (ULOQ Free CCL17: 3600 pg/mL, ULOQ Total CCL17: 50000 pg/mL).
 
Note: If more than 30% of values have been imputed at any timepoint for a treatment group, then the standard deviation is not displayed.
 
Note: Percentage reduction values ≤ 0 are imputed to be 0.1 and values ≥ 100 are imputed to be 99.9.
 
Note: The percentage reduction parameter was logit transformed, summarised, and back-transformed using the logistic function to obtain the geometric summary statistics. The 95% CI of the geometric mean was calculated using Student's t distribution.
	Part A SAC

No.	Population	IDSL / Example Shell	Title	Programming Notes	Deliverable

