			Fluid:Serum Free & Total CCL17 concentration ratio	
sd (logit), geometric mean and 95% CI back-transformed from the logit scale.
 
If % reduction ≤ 0, set to 0.1.
 
If % reduction ≥ 100, set to 99.9.
 
These imputations are needed for logit transformation.
 
Use Student's t-distribution for CI.
 
Please only present the median, min, max, sd (log), geometric mean and 95% CI back-transformed from the loge scale.
 
Apply logit transformation for % reduction parameter and present median, min, max, sd (logit), geometric mean and 95% CI back-transformed from the logit scale.
 
If % reduction ≤ 0, set to 0.1.
 
If % reduction ≥ 100, set to 99.9.
 
These imputations are needed for logit transformation.
 
Use Student's t-distribution for CI.
 
Add the following footnotes:
 
Note: Free CCL17 values below the LLOQ have been imputed to $\frac{1}{2}^*LLOQ$. Total CCL17 values below the LLOQ have been imputed to 0. Values equal to zero at baseline have been imputed to LLOQ whilst missing baseline values have been imputed to the median of the non-missing baseline values.
 
Note: Free CCL17 and Total CCL17 exceeding the upper limit of quantification (ULOQ) have been excluded from the summary statistics (ULOQ Free CCL17: 3600 pg/mL, ULOQ Total CCL17: 50000 pg/mL).
 
Note: If more than 30% of values have been imputed at any timepoint for a treatment group, then the standard deviation is not displayed.
 
Note: Percentage reduction values ≤ 0 are imputed to be 0.1 and values ≥ 100 are imputed to be 99.9.
 
Note: The percentage reduction parameter was logit transformed, summarised, and back-transformed using the logistic function to obtain the geometric summary statistics. The 95% CI of the geometric mean was calculated using Student's t
	

CONFIDENTIAL

207804

No.	Population	IDSL / Example Shell	Title	Programming Notes	Deliverable
				distribution.	
Immunogenicity					
4.05	Safety	IMM1	Part A: Summary of Immunogenicity		Part A SAC

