4.05.	Safety	PK17	Part B: Mean Free & Total Serum CCL17 Concentration-Time Plots (Linear and Semi-log)	
Apply logit transformation for % reduction parameter. If % reduction ≤ 0, set to 0.1. If % reduction ≥ 100, set to 99.9. These imputations are needed for logit transformation. Use Student's t-distribution for CI. Add the following footnotes: Note: Free CCL17 LLOQ = 2.93 pg/mL, ULOQ = 3600 pg/mL. Note: Total CCL17 LLOQ = 13.11 pg/mL, ULOQ = 50000 pg/mL. Note: Free CCL17 and Total CCL17 concentrations below LLOQ have been set to $\frac{1}{2} \times \text{LLOQ}$ and 0, respectively, and have been included in the summary statistic calculations. Note: Any single mid-profile non-quantifiable (NQ) concentrations have been omitted. Note: Measurable Total CCL17 concentrations following more than one consecutive mid-profile NQ have been omitted. Note: Zero Total CCL17 concentration values have been set to missing in the log-linear plot. Note: The geometric mean is plotted as the data is not normally distributed. Note: Percentage reduction values ≤ 0 are imputed to be 0.1 and values ≥ 100 are imputed to be 99.9. Note: The percentage reduction parameter was logit transformed, summarised, and back-transformed using the logistic function to obtain the geometric summary statistics.
	Part B SAC

No.	Population	IDSL / Example Shell	Title	Programming Notes	Deliverable
4.06.	Safety	PK18	Part B: Median Free & Total Serum CCL17 Concentration-Time Plots (Linear and Semi-log)	
Add the following footnotes:
 
Note: Free CCL17 LLOQ = 2.93 pg/mL, ULOQ = 3600 pg/mL.
 
Note: Total CCL17 LLOQ = 13.11 pg/mL, ULOQ = 50000 pg/mL.
 
Note: Free CCL17 and Total CCL17 concentrations below LLOQ have been set to $\frac{1}{2} \times \text{LLOQ}$ and 0, respectively, and have been included in the summary statistic calculations.
 
Note: Any single mid-profile non-quantifiable (NQ) concentrations have been omitted.
 
Note: Measurable Total CCL17 concentrations following more than one consecutive mid-profile NQ have been omitted.
 
Note: Zero Total CCL17-concentration values have been set to missing in the log-linear plot.
	Part B SAC

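### Post-baseline Total CCL17 below the LLOQ is set to 0 in displays that require a geometric mean, and in the tables also SD(log) and a log-scale 95% CI, which a zero does not allow

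*SAP*

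**What the plan says.** The instruction for Table 4.01 (Part A serum) reads "Please only present the median, min, max, sd (log), geometric mean and 95% CI", back-transformed from the natural-log scale. Table 4.03 (Part A blister fluid), Table 4.04 (Part A, "Fluid:Serum Free & Total CCL17 concentration ratio") and Table 4.06 (Part B serum) carry the same instruction. It covers Free and Total CCL17.

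The footnotes to these tables set Free CCL17 below LLOQ to half the LLOQ. For Total CCL17 they say "Total CCL17 values below the LLOQ have been imputed to 0". The only exception concerns baseline: "Values equal to zero at baseline have been imputed to LLOQ whilst missing baseline values have been imputed to the median". The median meant is that of participants who have a baseline value. A further note hides the standard deviation when more than 30% of a group's values at a timepoint are imputed.

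The mean figures (4.02 for Part A, 4.05 for Part B) say that Free and Total values below LLOQ were set to half LLOQ "and 0, respectively, and have been included in the summary statistic calculations". They add: "The geometric mean is plotted as the data is not normally distributed". Two notes limit this in the figures: "Any single mid-profile non-quantifiable (NQ) concentrations have been omitted" and "Zero Total CCL17 concentration values have been set to missing in the log-linear plot".

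**The concern.** The logarithm of 0 does not exist, so the table notes prescribe a value that their own required statistics cannot accept. The SAP deals with the same difficulty elsewhere in these notes. Free CCL17 gets a positive value, and percentage reduction is held between 0.1 and 99.9 because the logit needs it. Post-baseline Total CCL17 gets no such treatment.

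Target engagement is a secondary objective in both parts. A programmer who follows the notes literally cannot produce the SD or the CI for an affected cell. Another, whose software treats ln(0) as missing, will report a geometric mean of the quantifiable values only, with no sign that the low values were lost. Two people working from one plan could publish different numbers.

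**Working it through.** The plan gives no numerical result here to reproduce. The check is whether the required statistics exist, and how far the possible workarounds differ.

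**Inputs from the documents.** Total CCL17 LLOQ in serum is 13.11 pg/mL (SAP figure notes), so half LLOQ is 13.11 / 2 = 6.555. Part A has 6 active participants per cohort and 12 on placebo overall (Protocol 4.2). Part B has about 50 participants at 1:1, so about 25 per arm.

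**Formulas.** Geometric mean = exp(mean of ln x). SD(log) = SD of ln x. 95% CI = exp(mean ± t(0.975, n−1) × SD/√n).

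**Example.** Assumed serum values without drug accumulation, n = 12: one value below LLOQ, then 15, 18, 22, 25, 30, 35, 40, 50, 60, 75 and 100 pg/mL.

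| Handling of the low value | Mean ln | Geometric mean | SD(log) | 95% CI |
|---|---|---|---|---|
| 0, as written | −∞ | 0 | not computable | not computable |
| Dropped (n = 11) | 3.589 | 36.2 | 0.60 | 24.2 to 54.2 |
| Half LLOQ (n = 12) | 3.447 | 31.4 | 0.76 | 19.4 to 50.8 |

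The median is 32.5 with the zero kept or with half LLOQ.

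**Size of the dropping bias.** Assume lognormal data with SD(log) = s and a share p below LLOQ, and let z = Φ⁻¹(p). Dropping multiplies the geometric mean by exp(s·φ(z)/(1−p)). For p = 5, 10 and 20% the factor is 1.067, 1.124 and 1.234 with s = 0.6, and 1.115, 1.215 and 1.419 with s = 1.0. Half LLOQ gives 0.978, 0.960 and 0.931, and 0.986, 0.978 and 0.973. So dropping raises the geometric mean by 7 to 42%, while half LLOQ lowers it by 1 to 7%. The true geometric means implied by these cases are 21.7 to 67.9 pg/mL, so they describe placebo or other samples without accumulation.

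**Chance that a cell is affected.** With an assumed share p, the chance of at least one value below LLOQ is 1 − (1 − p)ⁿ.

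| n | p = 1% | 2% | 5% | 10% |
|---|---|---|---|---|
| 6 (Part A active cohort) | 5.9% | 11.4% | 26.5% | 46.9% |
| 12 (Part A placebo) | 11.4% | 21.5% | 46.0% | 71.8% |
| 25 (Part B arm) | 22.2% | 39.7% | 72.3% | 92.8% |

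The documents do not give p. On active drug it may be close to zero.

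**Do the other rules help?** The 30% rule is not triggered at 1/6 = 16.7%, 3/12 = 25% or 7/25 = 28%. It never suppresses the geometric mean or the CI. The omission of single mid-profile values appears in the figure notes, not the table notes, and leaves runs of two or more as zeros. Setting zeros to missing applies only to the log-linear plot, so the geometric mean in the linear plot keeps the problem.

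**The case against.** The best counter-argument is that the governing text cannot be seen. SAP 10.1.1.1 sends concentration handling to Section 14.5.4, which is not in the public text, and the blister target-engagement section is redacted. The drug-concentration displays (Table 3.01, Figure 3.02) show a similar zero convention under a house standard, which may say how zeros enter log statistics. Zero also has a legitimate use for the median and minimum in the same table. This lowers certainty, but a different rule in 14.5.4 would conflict with these explicit notes and would have to be reconciled with them. The redaction does mean that the absence of a blister-fluid LLOQ from the visible text is not a fault.

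On Table 4.04, the SAP makes the blister-to-serum ratio conditional on the data allowing it, which largely answers a zero serum denominator. It does not answer a zero blister value, which gives a ratio of 0 that cannot be logged.

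On reach, Protocol 4.4.1 describes high accumulation of total CCL17 in monkeys on drug, so active groups are less likely to be affected. That stands.

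A reader might infer that the target-engagement conclusions or an interim decision are compromised. The documents do not support that. Table 4.06 is delivered only at the final Part B analysis. The target-engagement table supplied at the third interim analysis (Table 4.07) is model-derived, as are the Part B percentage reduction and fold increase. No hypothesis test is attached to these summaries.

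**Conclusion.** The contradiction is real, and its importance is minor. Read as written, Tables 4.01, 4.03 and 4.06, and Table 4.04 where a ratio is formed, cannot deliver SD(log) or the CI for any cell holding a post-baseline Total CCL17 value of 0, and the geometric mean there is 0. The geometric mean in Figures 4.02 and 4.05 has the same defect for zeros not removed by the figure rules. If zeros are dropped instead, the geometric mean rises by 7 to 42% under the assumed lognormal cases with 5 to 20% below LLOQ.

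The cells most plausibly affected are placebo or other samples without drug accumulation. All shares below LLOQ and all distributions used here are assumptions; if no post-baseline Total value is below LLOQ, nothing changes. Median, minimum, maximum, Free CCL17, Part B model-based parameters, and the pain and safety analyses are unaffected.

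**What to change.** For the log-scale statistics in Tables 4.01, 4.03, 4.04 and 4.06 and for the geometric means in Figures 4.02 and 4.05, replace post-baseline Total CCL17 below LLOQ by half the LLOQ (6.555 pg/mL in serum), as already done for Free CCL17. Apply it before any blister-to-serum ratio is formed. Show the number of values below LLOQ by visit and arm, and align the notes with Section 14.5.4. The zero may stay in the individual and median displays, with a footnote saying that the log-scale statistics use a different value.

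The cost is a change to programming notes. Half LLOQ is a single-value imputation. With baseline zeros kept at LLOQ, a participant who is never quantifiable shows an artificial fall from 13.11 to 6.555 pg/mL (from 13.11 to 0 under the present rule), which is why the counts must stand beside the summaries. Reporting only median and range with those counts would also remove the contradiction, but would give up the geometric mean and CI that the plan asks for.

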4.4. Justification for Dose

4.4.1. Part A

Dose levels for Part A were selected on the basis of PK/PD predictions and preclinical data, which are summarised in Table 2. Please refer to the IB for further details.

A target mediated drug disposition model (TMDD) has been developed to characterise the aCCL17 PK and chemokine kinetics observed pre-clinically, and the model parameters were allometrically scaled to a 70 kg human [CP2015PK-002, 2016]. The estimated chemokine degradation rate (Kdeg=585.6/day) implies a chemokine half-life of approximately 2 minutes, considerably shorter than the 20-30 minutes expected. However, the estimated degradation rate (Kdeg) is derived by the assumption of low levels of serum CCL17 in equilibrium with extra cellular component, hence high accumulation of total (as observed in cynomolgus monkey) is explained by low CCL17 level and extremely high turnover. An alternative hypothesis is to assume a lower degradation rate and a much larger extra-cellular component outside plasma. An alternative model assuming a different chemokine degradation rate with a 10-minute half-life has been also developed. There are no differences in the estimated PK profiles for GSK3858279. The lower chemokine degradation rate also results in a longer return to baseline for the free chemokine profiles and sustained target engagement over a longer period. Predictions and safety margins are summarized in Table 2.

The 'Minimal Anticipated Biological Effect Level' (MABEL), as per Guideline on Strategies to Identify and Mitigate Risks for First-In-Human Clinical Trials with Investigational Medicinal Products [CHMP, 2017] was used to define the starting dose and is defined as the dose level predicted to result in a maximum inhibition in plasma in the 30-50% range. A dose of 0.1 mg/kg was designated the MABEL dose as the maximum predicted PD inhibition was 56%, according to human PK/PD predictions.

According to this model, the highest planned dose 10 mg/kg IV is expected to provide a maximum target engagement of 99% with half of this level being recovered after 9.5 days, and a return to baseline around three weeks post dose. Even at this highest simulated dose, high target engagement was not maintained over a 28-day period.

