10.1.1.2.2. Part B

All Target Engagement parameters in Part B will be calculated using a model based post-hoc analysis and the currently supported version of NONMEM. The model based post-hoc analysis is described in Section 11. All calculations will be based on actual sampling times.

Target Engagement parameters that will be calculated for free CCL17 in Part B are listed

CCI

CCI

[figure not shown]
NOTES:

Additional parameters may be included as required.

¹In the event that a robust and predictive population PK/TE model cannot be developed e.g. data limited by high levels of NR data, TE parameters will be derived directly from the observed data.

Target engagement parameters that will be calculated for total CCL17 in Part B are listed below. Additional parameters may be included as required.

CCI

NOTES:

Additional parameters may be included as required.

¹In the event that a robust and predictive population PK/TE model cannot be developed e.g. data limited by high levels of NR data, TE parameters will be derived directly from the observed data.

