14.6.4. Safety

ECG Parameters	
RR Interval	

 IF RR interval (msec) is not provided directly, then RR can be derived as: 
 [1] If QTcB is machine read & QTcF is not provided, then : $RR = \left[\left(\frac{QT}{QTcB} \right)^2 \right] * 1000$ 	

 [2] If QTcF is machine read and QTcB is not provided, then: $RR = \left[\left(\frac{QT}{QTcF} \right)^3 \right] * 1000$	

 if both the QTcB and QTcF values are machine read and provided, RR will not be calculated. If ECGs are manually read, the RR value preceding the measurement QT interval should be a collected value, THEN do not derive. 	
Corrected QT Intervals	

 When not entered directly in the eCRF, corrected QT intervals by Bazett's (QTcB) and Fredericia's (QTcF) formulas will be calculated, in msec, depending on the availability of other measurements. IF RR interval (msec) is provided then missing QTcB and/or QTcF will be derived as: 	
$QTcB = \frac{QT}{\sqrt{\frac{RR}{1000}}}$ $QTcF = \frac{QT}{\sqrt[3]{\frac{RR}{1000}}}$	
Worst Case Rules	

Worst case finding based on the interpretation and the clinical significance:
 
 Count the subject as 'ABNORMAL' and 'CLINICALLY SIGNIFICANT', if any of the findings are 'ABNORMAL' and 'CLINICALLY SIGNIFICANT' during the time period/Post-Baseline. Else count the subject as 'ABNORMAL' and 'NOT CLINICALLY SIGNIFICANT', if any of the findings are 'ABNORMAL' and 'NOT CLINICALLY SIGNIFICANT' and none of the findings are 'ABNORMAL' and 'CLINICALLY SIGNIFICANT' during the time period/Post-Baseline. Else count the subject as 'NORMAL' if there is a finding of 'NORMAL' and none of the findings are 'ABNORMAL' during the time period/Post-Baseline. Otherwise, do not count the subject during the time period/Post-Baseline, i.e. little n will reflect that the subject is not counted in the time period/Post-Baseline.. 	

Laboratory Parameters	

 All BLQ values will be imputed with $\frac{1}{2}$ LLOQ. All ALQ values will be imputed with the ALQ + [smallest positive number with the same number of decimal places as the ALQ is reported with] Values reported as $< x$ are assumed to have an LLOQ of x. Values reported as $> x$ are assumed to have an ALQ of x. 	

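### Dropping CCL17 values above the ULOQ from the observed concentration summaries (SAP Tables 4.01, 4.03, 4.06) biases those summaries low wherever any value exceeds the limit

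*SAP*

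**What the plan says.** The rule is in SAP 14.11.10.2, Table 4.06 (Part B serum free and total CCL17 by time): "Free CCL17 and Total CCL17 exceeding the upper limit of quantification (ULOQ) have been excluded from the summary statistics". The limits follow: "ULOQ Free CCL17: 3600 pg/mL, ULOQ Total CCL17: 50000 pg/mL". Part A Tables 4.01 (serum), 4.03 (blister fluid) and 4.04 (blister fluid:serum ratio) carry the same footnote. For the statistics shown, the programming note reads "Please only present the median, min, max, sd (log), geometric mean and 95% CI back-transformed from the" natural-log scale.

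Other provisions bear on this:

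- In the same tables, values below the LLOQ stay in: free CCL17 at half the LLOQ, total CCL17 at zero. If more than 30% of a cell is imputed, the SD is suppressed. Excluded values do not count towards that 30%.
- SAP 14.6.4 treats safety laboratory results above the limit differently: "All ALQ values will be imputed with the ALQ" plus the smallest increment at the reported precision.
- On Part B derived measures, SAP 10.1.1.2.2 says "All Target Engagement parameters in Part B will be calculated using a model based post-hoc analysis". The Table 4.06 footnote agrees: "Percentage reduction and fold increase parameters were calculated using a model based post-hoc analysis". If no robust model can be built, "TE parameters will be derived directly from the observed data".
- In Part A, SAP 10.1.1.2.1 takes target-engagement parameters directly from observed concentrations.
- The derived-parameter tables (4.02 and 4.07) do not state the exclusion.

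**The concern.** An assay result above the ULOQ says that the concentration is at least 50000 (or 3600) pg/mL. Removing it because it is high makes the exclusion depend on the outcome being summarised.

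For total CCL17 the upper tail is where the drug effect is expected. Protocol 4.4.1 refers to "high accumulation of total (as observed in cynomolgus monkey", and the SAP reports fold increase. What is left after exclusion is a truncated sample: its centre and spread are too low, and its printed maximum can never exceed the ULOQ.

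For free CCL17 the statistical bias is also downwards, but its meaning reverses. Protocol 4.4.2 describes engagement as the percentage reduction in free CCL17 from baseline. Losing high post-dose values on drug therefore makes engagement look greater. Losing high baseline values works the other way.

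The listed statistics include no count of values removed for this reason, so a reader of the table could not tell that a cell had been truncated.

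**Working it through.** The plan gives no figure to reproduce on this point. The check is closed-form algebra for a truncated normal on the log scale.

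**Inputs.** ULOQ for total CCL17 50000 pg/mL and the exclusion rule: SAP Table 4.06. Active arm of about 25 in Part B: Protocol 4.2 (about 50 participants, 1:1). Six active per Part A cohort: Protocol 4.2. Share *f* of a cell above the ULOQ, log SD *s*, and log-normality: assumed, because the documents give none of them. The ranges used are *f* = 1% to 20% and *s* = 0.5 to 1.0.

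**Formulas.** Let *z* be the normal quantile at 1 − *f*, φ the normal density at *z*, and λ = φ/(1 − *f*). Each ratio is to the true value.

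- Geometric mean after dropping: exp(−*s*λ)
- Median after dropping: exp(*s*·q), where q is the normal quantile at 0.5(1 − *f*)
- Log SD after dropping: √(1 − *z*λ − λ²)
- Geometric mean with the value set to the ULOQ: exp(*s*(*f z* − φ))

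**Worked case, *f* = 20%.** *z* = 0.842, φ = 0.280, λ = 0.280/0.80 = 0.350.

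- Geometric mean: exp(−0.5 × 0.350) = 0.839 and exp(−1.0 × 0.350) = 0.705.
- Median: q = −0.253, giving 0.881 and 0.776.
- Log SD: √(1 − 0.295 − 0.122) = 0.764.
- Set to the ULOQ: 0.20 × 0.842 − 0.280 = −0.112, giving 0.946 and 0.894.

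| Share above ULOQ | Geometric mean, dropped (*s* = 0.5 / 1.0) | Median, dropped (0.5 / 1.0) | Log SD, dropped | Geometric mean, set to ULOQ (0.5 / 1.0) |
|---|---|---|---|---|
| 0% | 1.000 / 1.000 | 1.000 / 1.000 | 1.000 | 1.000 / 1.000 |
| 1% | 0.987 / 0.973 | 0.994 / 0.988 | 0.968 | 0.998 / 0.997 |
| 5% | 0.947 / 0.897 | 0.969 / 0.939 | 0.900 | 0.990 / 0.979 |
| 10% | 0.907 / 0.823 | 0.939 / 0.882 | 0.844 | 0.977 / 0.954 |
| 20% | 0.839 / 0.705 | 0.881 / 0.776 | 0.764 | 0.946 / 0.894 |

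With values set to the ULOQ, the median is unbiased as long as fewer than half of the cell is above the limit.

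**Scale.** For 25 participants the 95% CI factor for the geometric mean is exp(2.064 × *s*/5): 1.229 at *s* = 0.5 and 1.511 at *s* = 1.0, or 0.206 and 0.413 on the log scale. At *f* = 20% the log bias is 0.175 and 0.350, about 85% of that half-width in both cases. At *f* = 1% it is 0.013 and 0.027, about 7%. In Part A one value out of six is 1/6 = 17% of a cell.

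**Table 4.04 is different.** A serum value above the ULOQ is the denominator. Excluding it removes a ratio that is low for that reason, so the summary tends to rise. Setting serum to the ULOQ would overstate that ratio. A blister value above the ULOQ acts in the opposite direction. No single direction or imputation applies.

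**The case against.** The strongest reply is that little depends on these cells. Target engagement is a secondary, descriptive objective. The Part B percentage reduction and fold increase come from the population model, and the interim delivery IA3 receives the model-derived Table 4.07, while Table 4.06 is produced only at the final Part B analysis. No decision rule in the documents uses observed total CCL17. Individual serum concentrations are listed (Listings 72 and 81) and individual profiles plotted. The Table 4.06 shell sits in a separate document and may print an n. There may be no value above 50000 pg/mL at all: the evidence for accumulation is one sentence about monkey data.

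Most of this stands and limits the point to observed concentration summaries. It does not justify the rule. A printed n would not separate a censored value from a missing sample, and listings do not correct a biased geometric mean.

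A reader might go further and infer that the exclusion removes participants, or that it makes the Part B target-engagement result too low. The documents support neither. The rule drops single values at a timepoint, and the participant's other timepoints remain. The model-derived measures are not shown to be affected, because the SAP does not say how the model treats values above the ULOQ. A reader might also expect dose groups to look artificially flat. That could arise only in Part A, since Part B has one active dose.

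**Conclusion.** The point holds for the observed concentration summaries in Tables 4.01, 4.03 and 4.06. Wherever a total CCL17 value exceeds 50000 pg/mL, the observed median, geometric mean, maximum and log SD at that timepoint are biased low. The geometric mean is about 1% too low at the mild end of the assumed range (1% above, log SD 0.5) and about 30% too low at the other end (20% above, log SD 1.0). If no value exceeds the limit there is no effect. These sizes rest on assumed log-normality, shares and SDs, and are illustrative.

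The direction in terms of engagement is not uniform: low for total CCL17, but overstated for free CCL17 when the dropped values are post-dose on drug. Part A, where parameters come from observed data, and the Part B observed-data fallback are more exposed than the default Part B model output. Even there, the documents do not say whether the derived parameters inherit the exclusion. A change is worth making because the rule deletes data by outcome, conflicts with the plan's own handling of other censored values, and is cheap to replace.

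**What to change.** In Tables 4.01, 4.03 and 4.06, replace the exclusion as follows:

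- Keep values above the ULOQ as right-censored. Either set them to the ULOQ, which is in line with the 14.6.4 laboratory convention (that rule adds one reporting increment), or use a censored log-normal estimate.
- Print n (%) above the ULOQ for each arm and timepoint.
- Count these values in the 30% rule that suppresses the SD.
- Label the maximum as >ULOQ where it is censored.

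In Table 4.04, do not impute the ratio. Report how many ratios are affected and whether the numerator or the denominator was above the ULOQ.

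It would also help to state whether the CCL17 figures and the PK/TE model follow the same handling, since neither is specified.

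The cost is SAP footnotes and programming, with no new data. The downside of setting values to the ULOQ is that the geometric mean remains a lower bound when many values are censored (0.946 to 0.894 of the truth at 20% above, for log SD 0.5 to 1.0). The printed count makes that visible.
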